6.4.1. Withdrawal of Consent

Subjects who request to discontinue receipt of study treatment will remain in the study and must continue to be followed for protocol specified follow-up procedures. The only exception to this is when a subject specifically withdraws consent for any further contact with him or her or persons previously authorized by the subject to provide this information. Subjects should notify the investigator in writing of the decision to withdraw consent from future follow-up, whenever possible. The withdrawal of consent should be explained in detail in the medical records by the investigator, as to whether the withdrawal is only from further receipt of investigational product or also from study procedures and/or posttreatment study follow-up, and entered on the appropriate CRF page. In the event that vital status (whether the subject is alive or dead) is being measured, publicly available information should be used to determine vital status only as appropriately directed in accordance with local law.

7. ASSESSMENTS

Every effort should be made to ensure that the protocol-required tests and procedures are completed as described. However, it is anticipated that from time to time there may be circumstances outside of the control of the investigator that may make it unfeasible to perform the test. In these cases the investigator will take all steps necessary to ensure the safety and well-being of the subject. When a protocol-required test cannot be performed, the investigator will document the reason for this and any corrective and preventive actions that he or she has taken to ensure that normal processes are adhered to as soon as possible. The study team will be informed of these incidents in a timely manner.

For samples being collected and shipped, detailed collection, processing, storage, and shipment instructions and contact information will be provided to the investigator site prior to initiation of the study.

7.1. Efficacy Assessments

7.1.1. American College of Rheumatology (ACR) Assessments

The specific components of the ACR Assessments (ACR Core Dataset) that will be used in this study are:

1. Tender/Painful Joint count (TJC) (68).
2. Swollen Joint Count (SJC) (66).
3. Patient's Assessment of Arthritis Pain.
4. Patient's Global Assessment of Arthritis.
5. Physician's Global Assessment of Arthritis.

6. C-Reactive Protein (CRP), measured by high sensitivity methodology (hsCRP).
7. Erythrocyte Sedimentation Rate (ESR).
8. Health Assessment Questionnaire – Disability Index (HAQ-DI).

Components of the ACR Core Dataset will be collected at the visits indicated in the [Schedule of Activities](#) and [Section 6](#).

7.1.2. Tender/Painful Joint Count (68)

Sixty-eight (68) joints will be assessed by a blinded joint assessor to determine the number of joints that are considered tender or painful. The response to pressure/motion on each joint will be assessed using the following scale: Present/Absent/Not Done/Not Applicable (to be used for artificial or missing joints). Artificial joints will not be assessed.

The 68 joints to be assessed are:

- Upper Body: temporomandibular, sternoclavicular, acromioclavicular;
- Upper Extremity: shoulder, elbow, wrist (includes radiocarpal, carpal and carpometacarpal considered as one unit), metacarpophalangeals (MCP I, II, III, IV, V), thumb interphalangeal (IP), proximal interphalangeals (PIP II, III, IV, V), distal interphalangeals (DIP II, III, IV, V);
- Lower Extremity: hip, knee, ankle, tarsus (includes subtalar, transverse tarsal and tarsometatarsal considered as one unit), metatarsophalangeals (MTP I, II, III, IV, V), great toe interphalangeal (IP), proximal and distal interphalangeals combined (PIP II, III, IV, V).

7.1.3. Swollen Joint Count (66)

The blinded joint assessor will also assess joints for swelling using the following scale: Present/Absent/Not Done/Not Applicable (to be used for artificial or missing joints).

Sixty-six (66) joints will be assessed for swelling, the same as those listed above for tenderness/pain, except that the right and left hip joints are not included in the swollen joint count. Artificial joints will not be assessed.

7.1.3.1. Tender and Swollen Joint Counts (28)

The twenty-eight tender/painful joint count includes the following joints: shoulders, elbows, wrists, metacarpophalangeal joints (MCP), proximal interphalangeal joints (PIP), and knees. This count will be calculated by Pfizer from the 68 tender/painful joint count assessed by the blinded joint assessor as described in Section 7.1.2.

This measurement will include the same joints as described above for 28 tender / painful joint count, and will be calculated by Pfizer from the 66 swollen joint count assessed for swelling by the blinded joint assessor as described in Section 7.1.3.

7.1.4. Patient's Assessment of Arthritis Pain (PAAP)

Patients will assess the severity of their arthritis pain using a 100 mm visual analog scale (VAS) by placing a mark on the scale between 0 (no pain) and 100 (most severe pain), which corresponds to the magnitude of their pain (See [Appendix 9](#)). This assessment must be performed early in the clinic visit and before the subject has extensive contact with site personnel and/or investigator.

7.1.4.1. Patient's Global Assessment (PtGA) of Arthritis

Patients will answer the following question, "Considering all the ways your arthritis affects you, how are you feeling today?" The patient's response will be recorded using a 100 mm visual analog scale (VAS) (See [Appendix 10](#)). This assessment must be performed early in the clinic visit and before the subject has extensive contact with site personnel and / or investigator.

7.1.4.2. Physician's Global Assessment (PhGA) of Arthritis

The investigator will assess how the patient's overall arthritis appears at the time of the visit. This is an evaluation based on the patient's disease signs, functional capacity and physical examination, and should be independent of the Patient's Global Assessment of Arthritis. The investigator's response will be recorded using a 100 mm visual analog scale (VAS) (See [Appendix 11](#)).

7.1.4.3. C-Reactive Protein (CRP)

Samples for analysis of high sensitivity CRP (hsCRP) will be collected at the visits specified in the [Schedule of Activities](#) and [Section 6](#). The samples will be shipped to and analyzed by a central laboratory. After randomization, the investigator and Pfizer Study Personnel directly involved in the conduct of the trial will be kept blinded of the results of this test.

7.1.4.4. Erythrocyte Sedimentation Rate (ESR)

Samples for analysis of ESR will be collected at the visits specified in the [Schedule of Activities](#) and [Section 6](#). Details of the collection and processing of ESR samples will be specified in the Laboratory Manual. ESR will be analyzed by a local laboratory (results will be reported to the central laboratory) using the Westergren method. ESR kits will be provided by the central laboratory. The local laboratory will report results to the central laboratory. After Randomization, the Investigator and Pfizer study personnel directly involved in the conduct of the trial will be kept blinded of the results of this test.

7.1.4.5. Health Assessment Questionnaire – Disability Index (HAQ-DI)

The HAQ-DI assesses the degree of difficulty a patient has experienced during the past week in 8 domains of daily living activities: dressing and grooming, arising, eating, walking, hygiene, reach, grip, and other activities.¹³ Each activity category consists of 2-3 items. For each question in the questionnaire, the level of difficulty is scored from 0 to 3 with 0 representing "no difficulty," 1 as "some difficulty," 2 as "much difficulty," and 3 as "unable to do." Any activity that requires assistance from another individual or requires the use of an assistive device adjusts to a minimum score of 2 to represent a more limited

functional status. This questionnaire must be performed early in the clinic visit and before the subject has extensive contact with site personnel and / or investigator. The form should then be checked by the site staff for completeness. A copy of the questionnaire can be found in [Appendix 8](#). This must be performed early in the clinic visit and before the subject has extensive contact with site personnel and / or investigator.

7.1.5. Composite Efficacy Assessments Derived from the ACR Core Dataset

7.1.5.1. Simplified Disease Activity Index (SDAI) Assessment

The SDAI is a continuous composite measure derived components of the ACR Core Dataset. The SDAI will be calculated using the following formula:

$SDAI = TJC \text{ (using 28 joints)} + SJC \text{ (using 28 joints)} + PtGA \text{ (0–10 cm scale)} + PhGA \text{ (0–10 cm scale)} + \text{and hsCRP (mg/dL)}$.

7.1.5.2. ACR Responder Analysis

The American College of Rheumatology's definition for calculating improvement in RA (ACR20) is calculated as a 20% improvement in tender and swollen joint counts and 20% improvement in 3 of the 5 remaining ACR-core set measures: patient and physician global assessments, pain, disability, and an acute-phase reactant which for this study will be CRP. Similarly, ACR50 and ACR70 are calculated with the respective percent improvement. Components of the ACR Responder Index will be collected as indicated in the [Schedule of Activities](#).

7.1.6. Disease Activity Score (DAS) Assessments

The Disease Activity Score (DAS) assessment is a continuous composite measure derived using differential weighting given to each component. DAS28 is a measure based on 28 tender and swollen joint counts. DAS28 may be calculated with 3 components (not including assessment of an acute phase reactant) (DAS28-3) or 4 components (DAS28-4 = DAS28-3 + either ESR or CRP). The formulae for calculation of DAS28-4 (CRP) and DAS28-4 (ESR) are presented in [Appendix 7](#). Components of DAS-3, DAS28-4 (CRP), and DAS28-4 (ESR) will be collected as indicated in the [Schedule of Activities](#).

The components of the DAS 28 arthritis assessment include:

1. Tender/Painful Joint Count (28).
2. Swollen Joint Count (28).
3. CRP or ESR.
4. Patient's Global Assessment of Arthritis.

7.2. Patient Reported Outcomes (PROs)

7.2.1. SF-36 Health Survey (Version 2, Acute)

The SF-36 v.2 (Acute) is a 36-item generic health status measure. It measures 8 general health domains: physical functioning, role physical, bodily pain, general health, vitality, social functioning, role emotional and mental health. These domains can also be summarized as physical and mental component scores. This must be performed early in the clinic visit and before the subject has extensive contact with site personnel and / or investigator. The form should be checked for completeness by the site staff. A copy of the questionnaire can be found in [Appendix 12](#). The SF-36 will be collected as indicated in the [Schedule of Activities](#) and [Section 6](#).

7.2.2. Functional Assessment of Chronic Illness Therapy – Fatigue (FACIT-F)

The FACIT – F is a patient completed questionnaire consisting of 13 items that assess fatigue. Instrument scoring yields a range from 0 to 52, with higher scores representing better patient status (less fatigue). This questionnaire must be performed early in the clinic visit and before the subject has extensive contact with site personnel and/or investigator. The form should then be checked by site staff for completeness. A copy of the questionnaire can be found in [Appendix 13](#). The FACIT-F will be collected as indicated in the [Schedule of Activities](#) and [Section 6](#).

7.2.3. European Quality of Life – 5 Dimensions-3 Level (EQ-5D-3L)

The EQ-5D-3L Health State Profile is a patient completed questionnaire designed to assess impact on health-related quality of life in five domains: mobility, self-care, usual activities, pain/discomfort, and anxiety/depression. Additionally, scores from the five domains may be used to calculate a single index value, also known as a utility score. The validity and reliability of the EuroQol EQ-5D-3L has been established in a number of disease states, including rheumatoid arthritis. This questionnaire must be performed early in the clinic visit and before the subject has extensive contact with site personnel and / or investigator. The form should then be checked by site staff for completeness. A copy of the questionnaire can be found in [Appendix 14](#). The EQ-5D-3L will be collected as indicated in the [Schedule of Activities](#) and [Section 6](#).

7.3. Safety Assessments

Safety will be assessed by the spontaneous reporting of AEs, physical examinations, ECGs, and clinical laboratory results in all subjects who received at least 1 dose of study medication. Investigators and Pfizer Clinicians will review individual subject data throughout the conduct of the trial to ensure subjects' well-being.

7.3.1. Clinical Safety Laboratory Tests

The following safety laboratory tests will be performed at times defined in the [Schedule of Activities](#). Unscheduled clinical labs may be obtained at any time during the study to assess any perceived safety concerns.

Table 9. Safety Laboratory Tests

Hematology	Chemistry Panel	Urinalysis	Other
Hemoglobin	BUN/Urea & Creatinine	pH	FSH ^a
Hematocrit	Glucose (fasting)	Glucose	Pregnancy Tests ^b
RBC count	Calcium	Creatinine	
MCH	Sodium	Protein	HIV, HepBsAg,
MCHC	Potassium	Blood	HepBc Ab and
RBC morphology and MCV	Chloride	Ketones	HCVAb or HCV RNA
Platelet count	Total CO ₂ (Bicarbonate)	Nitrites	QuantiFERON [®] TB
WBC count	AST, ALT	Leukocyte esterase	Gold test ^d
Total neutrophils (Abs and %)	Total bilirubin	Urobilinogen	
Eosinophils (Abs and %)	Alkaline phosphatase	Urine bilirubin	
Basophils (Abs and %)	Uric acid	Color and clarity	
Lymphocytes (Abs and %)	Albumin	Specific gravity	
Monocytes (Abs and %)	Total protein	Microscopy	
Reticulocyte count WBEDT	Serum myoglobin ^d		
Reticulocyte count %	Lipid profiles ^c		
	Cardiac troponin-I (cTn-I), CK and CK-MB ^d		

- In females who are amenorrheic for at least 12 consecutive months.
- Urine pregnancy tests for women of childbearing potential.
- Lipid Profile includes fasting total cholesterol, LDL, HDL, triglycerides and may include fasting apolipoprotein A-1 and B and other lipoprotein tests potentially including particle size measurements.
- At screening only, additional tests may be performed during the study at the investigator's discretion, as indicated by signs and symptoms of ongoing AEs.

7.3.2. Physical Examination

Complete Physical Examination:

A standard physical examination will be performed at the visits identified in [SoA](#). The following parameters and body systems will minimally be examined and any abnormalities described: General appearance, skin (presence of rash), HEENT, lungs (auscultation), heart (auscultation for presence of murmurs, gallops, rubs, peripheral edema), abdominal (palpation and auscultation), neurologic (mental status, station, gait, reflexes, motor and sensory function, coordination) and, lymph nodes.

Weight will be recorded as listed in [Schedule of Activity](#).

Targeted Examination:

At all other visits, as defined in the [SoA](#), an abbreviated physical examination will be performed that will minimally include the following: Skin, lungs, heart, abdomen and lymph nodes. Additional organ systems may be examined at the investigator decision. Any clinically significant changes from the baseline examination should be recorded as AEs. Body temperature also will be collected at these visits.

7.3.3. Medical History

Medical history in addition to RA history including disease duration and extent of disease, cardiac history and smoking history will be collected at Screening. Height and weight will be measured without the subject wearing shoes. Height (inches or centimeters) and weight (lbs or kg) will be measured up to one decimal place and recorded in the source document at the screening visit.

7.3.4. Pregnancy Testing

All pregnancy tests used in this study, either urine or serum, must have a sensitivity of at least 25 mIU/mL and must be performed by a certified laboratory. For female subjects of childbearing potential, 2 negative pregnancy tests are required before receiving PF-06650833 (1 negative pregnancy test at screening and 1 at the baseline visit immediately before PF-06650833 administration). Following a negative pregnancy test result at screening, appropriate contraception must be commenced and the second negative pregnancy test result will then be required at the baseline visit and within 5 days after the first day of the menstrual period (counting the first day of the menstrual period as Day 1) before the subject may receive the PF-06650833. In the absence of regular menstrual bleeding, the study candidate should have used 2 forms of contraception for at least 1 month before the second pregnancy test. Pregnancy tests will also be repeated at all visits and at the end of the study to confirm that the subject has not become pregnant during the study. Pregnancy tests will also be done whenever 1 menstrual cycle is missed during the active treatment period and when potential pregnancy is otherwise suspected, and may be repeated if requested by institutional review boards (IRBs)/ethics committees (ECs) or if required by local regulations. In the case of a positive confirmed pregnancy, the subject will be withdrawn from administration of investigational product and from the study.

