- g. Chest radiograph (posterior-anterior and lateral views are recommended, however local guidelines should be followed) is required at Screening. A chest X-ray or other appropriate diagnostic imaging modality (ie, CT or MRI) performed within 12 weeks prior to screening and read by a qualified radiologist with no evidence of current, active TB or previous inactive TB, general infections, heart failure or malignancy may substitute for the chest X-ray taken at Screening. Documentation of the official reading must be located and available in the source documentation.
- h. Laboratory tests may be repeated once during the screening period; the last value will be used to determine eligibility. Single repeats of laboratory tests are inclusive of Blood Chemistry, Hematology, C-Reactive Protein (hsCRP), Erythrocyte Sedimentation Rate (ESR), Anti CCP Antibodies (ACPA) and Urinalysis. Fasting lipid profile will be assessed at Baseline, Week 4 and Week 12 (samples must be collected after a minimum 6-hour fasting), and includes: fasting total cholesterol, LDL, HDL, triglycerides and apolipoproteins A-1 and B (and other lipoprotein tests potentially including particle size measurements). Laboratory tests at Weeks 6, 10, and 14 will only include standard blood chemistry panels (not hematology).
- i. ESR will be analyzed locally using the Westergren method. ESR kits will be provided by the central laboratory. ESR results will be reported to the central laboratory. After Randomization, the Investigator and Pfizer study personnel directly involved in the conduct of the trial will be kept blinded of the results of this test.
- j. Collect pre-dose urine sample for central laboratory urinalysis and urine microscopy.
- k. Required for women of childbearing potential that are not surgically sterilized or do not meet the definition of menopause as per the inclusion/exclusion criteria. Pregnancy test must be performed as described in [Section 7.3.4](#) and be negative prior to randomization on Day 1. A delay in randomization for WOCBP in order to collect the second pregnancy test within 5 days after the first day of the menstrual period will not be considered a protocol deviation (PD).

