4.1. Inclusion Criteria

Subjects must meet all of the following inclusion criteria to be eligible for enrollment into the study:

1. Evidence of a personally signed and dated informed consent document indicating that the subject has been informed of all pertinent aspects of the study.
2. Willing and able to comply with scheduled visits, treatment plan, laboratory, and other study procedures.

3. Male and female (including WOCBP) subjects between the ages of 18 and 75 years, inclusive. For subjects >70 years old, the site must discuss subject eligibility with the study team to ensure that these subjects are sufficiently healthy to participate.
4. Female subjects of childbearing potential must test negative for pregnancy at screening visit and baseline visit.
5. Female subjects of nonchildbearing potential must meet at least 1 of the following criteria:
 - a. Achieved postmenopausal status, defined as follows: cessation of regular menses for at least 12 consecutive months with no alternative pathological or physiological cause; and have a serum follicle-stimulating hormone (FSH) level confirming the postmenopausal state;
 - b. Have undergone a documented hysterectomy and/or bilateral oophorectomy;
 - c. Have medically confirmed ovarian failure.

All other female subjects (including female subjects with tubal ligations) are considered to be of childbearing potential.

6. Diagnosis of RA and meeting the 2010 American College of Rheumatology (ACR)/European League Against Rheumatism (EULAR) classification criteria (see [Appendix 2](#)) for RA with a Total Score $\geq 6/10$. The duration of time since diagnosis of RA should minimally be sufficient to meet the definition of methotrexate inadequate response (MTX-IR) (see below).
7. The subject has active disease at both Screening and Baseline, as defined by both:
 - ≥ 6 joints tender or painful on motion, AND
 - ≥ 6 joints swollen;

and fulfills 1 of the following 2 criteria at Screening:

 - High sensitivity C reactive protein (hsCRP) >7 mg/L at screening performed by the central laboratory. Subjects who do not meet this entry criterion but satisfy all other study entry criteria may have serum hsCRP concentration re-tested once within 14 days and, if the repeat hsCRP concentration is >7 mg/L will be eligible to enroll into the study provided all other inclusion/exclusion criteria are met.
 - Erythrocyte sedimentation rate (ESR) (Westergren method) >28 mm/hr;

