- Complete Physical Examination, minimally including: vital signs, general appearance, skin (presence of rash, skin lesions with malignant features), HEENT (head, eyes, ears, nose and throat), lungs (auscultation), heart (auscultation for presence of murmurs, gallops, rubs), lower extremities (peripheral edema), abdominal (palpation and auscultation), neurologic (mental status, station, gait, reflexes, motor and sensory function, coordination) and lymph nodes. (Additional brief PE may be performed during the study at the investigator's discretion);
- 12-lead electrocardiogram [An ECG may be performed at other times, at the discretion of the Investigator if there were findings during a previous examination or in the case of a new/open adverse event (AE)];
- Chest radiograph (posterior-anterior and lateral views are recommended, however local guidelines should be followed) is required at Screening. A chest X-ray or other appropriate diagnostic chest imaging modality [ie, Computerised Tomography (CT) or Magnetic Resonance Imaging (MRI)] performed within 12 weeks prior to screening and read by a qualified radiologist with no evidence of current, active TB or previous inactive TB, general infections, heart failure or malignancy may substitute for the Chest X-ray taken at Screening. Documentation of the official reading must be located and available in the source documentation;
- Collect blood samples for clinical chemistry (including hsCRP) and hematology;
- Collect blood sample for local ESR testing;
- Collect blood sample for RF, ACPA;
- Collect blood samples for HIV Serology, HBsAg, HBcAb, HBsAb, HCV Ab or HCV RNA; Human immunodeficiency virus (HIV) testing is mandatory; however reporting of results should be handled per local regulations;
- Collect blood sample for FSH (Women of Non Child Bearing Potential (WONCBP), only);
- Collect blood for tuberculosis (QuantiFERON Gold[®]™ In-Tube) test: Unless tested and documented within 3 months of screening visit;
- CCI [REDACTED]
- Collect urine sample for urinalysis (proteinuria, pH color, clarity) and urine microscopy;
- Urine pregnancy testing must be completed for all women of childbearing potential; A delay in randomization for WOCBP in order to collect the second pregnancy test within 5 days after the first day of the menstrual period will not be considered a protocol deviation (PD);

- Confirm proper contraception is being used;
- CCI [REDACTED]
- CCI [REDACTED]

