6.2. Study Period

Study visits are calculated from Visit 2 Baseline/Day 1/Week 0. Visit dates and windows are anchored on the first day of dosing. All visits should be conducted as close to the scheduled visit day as possible. Exceptions may be made to accommodate holidays and unexpected events, such as weather-related site closures or illnesses requiring hospitalization. In these cases, the visit should be scheduled or re-scheduled as close to the original visit schedule as possible.

6.2.1. Visit 2, Baseline Day 1/Week 0

Patients are required to fast for at least 6 hours prior to the visit. The patient reported outcome (PRO) assessments (Patient Assessment of Arthritis Pain, Patient Global Assessment of Arthritis, Physician Global Assessment of Arthritis, Health Assessment Questionnaire - Disability Index (HAQ-DI), SF-36 Version 2 (Acute), FACIT Fatigue Scale, EuroQol EQ-5D-3L) should be done before other study-related procedures and before significant contact with the principal investigator (PI) and site personnel. Vital signs, physical examination and ECG, should be conducted next.

The Investigator will review all inclusion/exclusion criteria. If the subject is eligible to continue, the following should be conducted:

Procedures that will be performed predose:

- ACR/DAS Assessments: Tender/Painful Joint Counts (68), Swollen Joint Count (66), Patient Assessment of Arthritis Pain, Patient Global Assessment of Arthritis, Physician Global Assessment of Arthritis, Health Assessment Questionnaire – Disability Index (HAQ-DI);
- Collect additional PROs: SF-36 Version 2 (Acute), FACIT-fatigue scale, EQ-5D-3L;
- Prior Medication and Treatments (RA and non RA): Current and prior medications (noting exclusions and required DMARD restrictions) taken with reasons and should include dose/duration;
- Measure vital signs: sitting blood pressure, pulse, and temperature (tympanic, oral, axillary, or temporal);

- Perform targeted physical examination;
- Perform 12-lead electrocardiogram;
- Collect blood samples for chemistry (including hsCRP) and hematology laboratory assessments;
- Collect blood sample for local ESR assessment;
- Collect blood samples for RF, ACPA;
- Collect blood sample for immunoglobulin Ig (IgA, IgM, IgG, IgE) analyses;
- Collect urine sample for central laboratory urinalysis and urine microscopy;
- Confirm proper contraception is being used;
- Collect urine for local urine pregnancy testing (women of childbearing potential, only);

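### Footnote k of the Schedule of Activities scopes pregnancy testing by an undefined sterilization term that does not match inclusion 4–5 and Section 7.3.4, so sites could test women with tubal procedures inconsistently

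*Protocol*

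**What the plan says.** Who is of childbearing potential is settled in protocol Section 4.1, inclusion 5. There are three routes out of the group: confirmed postmenopausal status, medically confirmed ovarian failure, and one surgical route, "Have undergone a documented hysterectomy and/or bilateral oophorectomy". The criterion then closes: "All other female subjects (including female subjects with tubal ligations) are considered to be of childbearing potential".

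Who is tested is stated in several places:

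- Inclusion 4: "Female subjects of childbearing potential must test negative for pregnancy at screening visit and baseline visit".
- Section 6.1, at screening: "Urine pregnancy testing must be completed for all women of childbearing potential".
- Section 6.2.1, before the first dose, and the later visit lists: local urine testing for women of childbearing potential.
- Section 7.3.4: "For female subjects of childbearing potential, 2 negative pregnancy tests are required before receiving PF-06650833", with the test repeated at all visits and at the end of the study.
- Schedule of Activities, footnote k, attached to the urine pregnancy test row: "Required for women of childbearing potential that are not surgically sterilized or do not meet the definition of menopause as per the inclusion/exclusion criteria". Its next sentence refers to Section 7.3.4 for how the test is performed and adds that it must "and be negative prior to randomization on Day 1".

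Section 4.3 requires every inclusion criterion to be met at randomization. Section 4.4.1 states a potential for teratogenicity for both PF-06650833 and tofacitinib, and lists tubal ligation, bilateral salpingectomy and tubal occlusion as highly effective contraceptive methods.

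**The concern.** Four of these places take the childbearing-potential group as inclusion 5 defines it and test all of it. Footnote k starts from the same group and adds a qualifier about surgical sterilization. Inclusion 5 has already removed women with hysterectomy or bilateral oophorectomy. The sterilized women who remain are therefore essentially those with a tubal procedure, and the ordinary sense of the phrase covers them.

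The schedule table is a page that site staff are likely to work from visit by visit. A site that takes its testing population from footnote k may leave these women out, while a site that takes it from Section 7.3.4 tests them. At stake are an eligibility criterion left unmet, different handling of identical women, and a missed check before and during exposure to drugs for which the protocol states a fetal risk.

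**Working it through.** The plan gives no figure to reproduce. The check is a comparison of texts plus one line of arithmetic.

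**Does footnote k exempt a premenopausal woman with tubal ligation?** Two points are open: whether its *or* is literal or means neither/nor, and whether surgical sterilization includes tubal procedures or only those named in inclusion 5b.

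| Reading of *or* | Sterilization means | Result for this woman |
|---|---|---|
| Literal | includes tubal procedures | Tested: she does not meet the definition of menopause |
| Literal | inclusion 5b only | Tested |
| Neither/nor | inclusion 5b only | Tested: she is neither |
| Neither/nor | includes tubal procedures | Exempt |

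One combination of four exempts her. The first three, however, leave the qualifier with no effect. With a literal *or*, every woman of childbearing potential qualifies through the menopause clause, because inclusion 5a has already taken out those who meet it. With sterilization limited to inclusion 5b, no sterilized woman remains in the group. Only the fourth reading gives the sterilization words any work to do. Section 4.4.1 leans the same way on usage, since it applies the word sterilization to vasectomy, the male counterpart of a tubal procedure.

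**What do the other texts require of her?** Under inclusion 5 she is of childbearing potential. Inclusion 4 with Section 4.3 then requires negative tests at screening and baseline before she can be randomized, and Sections 6.1, 6.2.1 and 7.3.4 agree. Under all four readings of footnote k, dosing her untested is a protocol deviation.

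**How many tests are in question?** The urine pregnancy test row is marked at Visits 1 to 10 and at early withdrawal. Under the fourth reading, a woman who completes the study would have none of 10 scheduled tests; under the other three she would have all 10.

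**How large is the pregnancy risk?** Inputs: a failure rate below 1% per year under perfect use (Section 4.4.1), and about 20 weeks of participation (Section 3: up to 4 weeks of screening, 12 of treatment, 4 of follow-up). Assuming a constant rate over the year:

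1% × 20/52 = 0.38%, so below about 0.4% per woman.

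This is an upper bound on pregnancy in such a woman during the study, with or without testing. It is not the risk added by leaving the test out.

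**The case against.** The strongest reply is that footnote k is only a loose restatement of the definition. Its menopause clause is redundant on any reading, so the sterilization clause may be redundant too, as shorthand for inclusion 5b. Its closing reference to the eligibility criteria can be taken to cover both clauses, and inclusion 5 settles tubal ligation expressly. The footnote never names tubal procedures. Its next sentence refers to Section 7.3.4, and the text before the table calls the schedule an overview and sends readers to the detailed sections.

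Most of this stands, and it rules out three stronger conclusions that a reader might draw:

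- *The protocol allows these women to be dosed untested.* It does not. Inclusion 4 and Section 4.3 bar it, and an untested dose would be a deviation at a site that relied on the footnote alone.
- *Footnote k plainly exempts them.* It does so under one combination of readings out of four.
- *These women would be lost from the per-protocol set.* SAP Section 4.3 excludes major protocol violations without listing them, so this is conjecture.

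What does not stand is that the cross-reference removes the ambiguity. It follows the sentence saying for whom the test is required, and can be read as governing how the test is done rather than who has it. No passage says which text prevails on pregnancy testing, and the key term remains undefined.

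**Conclusion.** The point holds as an internal inconsistency with a real chance of misapplication. An operative footnote uses a scope term that is undefined and does not match inclusion 5, on a matter that is both an eligibility condition and a fetal-safety check. A site relying on footnote k alone could reasonably skip the test in women with tubal procedures, leaving inclusion 4 unmet and practice uneven across sites.

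The size is small. The pregnancy risk is below about 0.4% per woman over 20 weeks, assuming that the contraceptive failure bound in Section 4.4.1 applies at a constant rate. The number of women with tubal procedures is not given, so no study-level figure can be stated. The primary analysis is not affected: it uses the intent-to-treat set (SAP Sections 4.1 and 6.1.1), in which any randomized and dosed woman stays, tested or not. The point is worth correcting because it bears on safety and costs little, not because it threatens the trial's conclusions.

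**What to change.** Reconcile footnote k with inclusion 4–5 and Section 7.3.4, so that a single stated definition, by reference to inclusion 5, decides who is tested. The sponsor decides which wording stands:

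- If no exemption is intended, footnote k can drop its own qualifier and cite inclusion 5.
- If an exemption is intended, surgical sterilization needs a definition, and inclusion 4–5, Sections 6.1 and 7.3.4 and the visit lists must carry the same exemption.

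The first route costs one phrase in a footnote; the second costs matching edits in several sections. Neither adds a visit. The most that either could add in practice is urine tests at visits already scheduled, for women whom a site would otherwise have left out.
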